5.3 Participant Registration

5.3.1 Patient Registration

Eligible patients will be entered on study centrally by the Fox Chase Cancer Center QA Coordinator or their designee. Following registration, patients should begin protocol

treatment within 7 days of registration. If a patient does not receive protocol therapy following registration, the patient's registration on the study may be cancelled and the subject will be replaced. The QA Coordinator should be notified of cancellations as soon as possible.

Subjects may be registered from 9:00 am to 5:00 pm excluding holidays by calling the QA Coordinator at [contact]. The site's investigator or designee will then fax the completed registration form, consent and HIPAA signature pages and eligibility checklist to [contact]. The QA Coordinator or designee will notify the site by phone and fax when registration is confirmed and the sequence number has been assigned. Subjects must be registered and have received a sequence number assigned by the QA Coordinator prior to the initiation of treatment. The following forms must be completed at the time of registration:

- Signed and dated informed consent form
- Signed and dated HIPAA consent form
- Registration form
- Signed eligibility checklist

6 STUDY DRUG

6.1 Description of Investigational Agents

Ixazomib Capsules

The ixazomib drug product is provided in strengths of 4.0-, 3.0-, and 2.3-mg and 2.0-, 0.5-, and 0.2 mg capsules as the active boronic acid. The different dose strengths are differentiated by both capsule size and color as described below:

Dose Strength	Capsule Size	Capsule Color
4.0 mg	Size 4	Ivory
3.0 mg	Size 3	Light gray
2.3 mg	Size 2	Light pink
2.0 mg	Size 2	Swedish orange
0.5 mg	Size 3	Dark green
0.2 mg	Size 4	White opaque

For additional details, please see the Ixazomib IB.

Pegylated Interferon alpha 2b

The pIFN will be obtained commercially for each patient.

6.2 Study Drug Administration

Ixazomib Administration

All protocol-specific criteria for administration of study drug must be met and documented before drug administration. Study drug will be administered or dispensed only to eligible patients under the supervision of the investigator or identified subinvestigator(s). Patients should be monitored for toxicity, as necessary, and doses of ixazomib should be modified as needed to accommodate patient tolerance to treatment; this may include symptomatic treatment, dose interruptions, and adjustments of ixazomib dose (see Section 6.3).

Capsules of ixazomib will also be referred to as study drug. Study drug will be supplied by Millennium as capsules of 2.0 mg, 2.3 mg, 3.0, and 4.0 mg ixazomib. If during the dose escalation phase I we find that the lowest dose (ixazomib 2.3 mg and pIFN 3 μ g/kg/week) is not tolerable and have to dose de-escalate, we will use 0.5 mg capsules and the protocol will be amended. If the MTD in Phase I is found to be 2.3 mg, dose levels for phase II will be 2.3 mg, 2.0 mg and 1.5 mg.

The prescribed administration of ixazomib doses in this study is 1.5-4.0 mg ixazomib weekly for 3 out of 4 weeks in each cycle (1 cycle=28 days).

Patients should be instructed to swallow ixazomib capsules whole, with water, and not to break, chew, or open the capsules. Study drug should be taken on an empty stomach (no food or drink) at least 1 hour before or 2 hours after a meal. Each capsule should be swallowed separately with a sip of water. A total of approximately 8 ounces (240 mL) of water should be taken with the capsules.

Missed doses can be taken as soon as the patient remembers if the next scheduled dose is 72 hours or more away. A double dose should not be taken to make up for a missed dose. If the patient vomits after taking a dose, the patient should not repeat the dose but should resume dosing at the time of the next scheduled dose.

The patient will take the pill in clinic during the first 2 cycles and either in clinic or at home during all subsequent cycles depending on whether they are in clinic for a visit on a particular week or not. They will write down in a patient diary the time of administration and dose when taking at home.

Ixazomib Destruction

Investigational ixazomib (expired or end of study) should be destroyed on site according to the institution's standard operating procedure. The investigators will document removal and destruction on drug accountability logs.

Pegylated IFN- α -2b Administration

Pegylated IFN- α -2b (PegIntron): Each patient will be treated with Pegylated IFN- α -2b by subcutaneous injection in clinic by a registered nurse or at home by self-injection after proper training. They will write down in a patient diary the time of administration and dose

if they are injecting at home. The dose will be based on phase of study (see section 4-1). The drug will be obtained commercially in various vial strengths depending on patient's weight in kg (see below). The injection site will be rotated between thigh, outer surface of upper arm, and abdomen. Injections will not be given near navel or waistline; patients who are thin will only have thigh or upper arm used. No injection will be given into a bruised, infected, irritated, red, or scarred skin.

All patients will be pre-medicated with acetaminophen (500-1000 mg orally) 30 minutes prior to the first dose and as needed for subsequent doses thereafter.

Dose in mL=Weight (kg) x Dose (μ g/kg)/Reconstituted Vial Strength (μ g/mL)

For patients whose CrCl was acceptable for study eligibility/entry per a 24 hour urine creatinine clearance, but not Cockcroft-Gault, if serum creatinine increases by 20% or more, the dose of pegylated IFN will be reduced by 25% for the particular dose level the patient is at and not re-escalated.

If a patient's CrCl was acceptable per Cockcroft-Gault for study eligibility/entry, if CrCl drops to between 30-50 ml/min while on treatment, the dose of pegylated IFN will be reduced by 25% for the particular dose level the patient is at and not re-escalated.

6.3 Dose-Modification Guidelines

Treatment with Ixazomib and Pegylated IFN- α -2b will use a cycle length of 28 days. Evaluations will occur as listed in the Study Calendar. For a new treatment cycle to begin, the patient must meet the following criteria:

- ANC must be $\geq 1,000/\text{mm}^3$.
- Platelet count must be $\geq 75,000/\text{mm}^3$.
- Hemoglobin must be $\geq 8.0 \text{ g/dL}$.
- All other non-hematologic toxicity (except for alopecia) must have resolved to \leq Grade 1 or to the patient's baseline condition

If the patient fails to meet the above-cited criteria for initiation of the next treatment, dosing should be delayed for 1 week for both drugs. If the patient continues to fail to meet the above-cited criteria, delay therapy and continue to re-evaluate. The maximum delay before treatment should be discontinued will be 4 weeks or at the discretion of the Principal Investigator.

For dosing recommendations upon recovery, refer to Table 6-1, Table 6-2 and Table 6-3. If starting doses will be different than below, the protocol will be amended prior to moving on to Phase II.

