Table 6-1 MLN908 and Pegylated IFN- α -2b Dose Adjustments during Phase II: Note levels for dose modification do not correspond with levels for dose escalation. Dose modifications will depend on the RP2D. Final dose modification schedule will be decided upon once the RP2D is determined. As an example, if the RP2D is, as expected, 4.5 mcg/kg/week of pIFN and 4.0 mg per week of Ixazomib, then the dose modification schedule will be as below.

Dose Mod Level	pIFN Dose (mg)	Ixazomib Dose (mg)
1	4.5 mcg/kg/week	4.0 mg
-1	3.0 mcg/kg/week	3.0 mg
-2	1.0 mcg/kg/week	2.3 mg
-3	Discontinue	Discontinue

Table 6-2 Ixazomib and Pegylated IFN- α -2b Dose Adjustments for Hematologic Toxicities

Within-Cycle Dose Modifications	

 • If platelet count $\leq 75 \times 10^9/L$ or ANC $\leq 0.50 \times 10^9/L$ on a Ixazomib dosing day (other than Day 1 (if Day 1, see section 6.3)) 	
 • Ixazomib dose should be withheld. • Complete blood count (CBC) with differential should be repeated at least every other day until the ANC and/or platelet counts have exceeded the prespecified values (see Section 6.3.1) on at least 2 occasions. • Upon recovery, Ixazomib may be reinitiated with 1 dose level reduction.

 • If ANC $\leq 0.50 \times 10^9/L$ and the patient is febrile (febrile neutropenia) 	
 • All treatment suspended until ANC count has exceeded the prespecified value (see Section 6.3.1) on at least 2 occasions. • Upon recovery, Ixazomib and pegylated IFN may be reinitiated with 1 dose level reduction.
Dose Modifications for Subsequent Treatment Cycles	

 • Delay of > 2 weeks in the start of a subsequent cycle due to lack of toxicity recovery as defined in Section 6.3Error! Reference source not found. • ANC $< 1.0 \times 10^9/L$, platelet count $< 75 \times 10^9/L$, or other non-hematologic toxicities $>$ Grade 2 or not to the patient's baseline condition 	
 • Hold Ixazomib until resolution as per criteria Section 6.3. • Upon recovery, reduce Ixazomib 1 dose level. • The maximum delay before treatment should be discontinued will be 3 weeks or at the discretion of the PI.
Dose Modifications for Subsequent Treatment Cycles	

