Grade 3 diarrhea	
 • Hold Ixazomib AND Interferon until resolution to Grade ≤ 1 or baseline. Initiate symptomatic recommendations as per Section 6.4. • Reduce both drugs to next lower dose upon recovery. 	
Grade 4 diarrhea	
 • Hold Ixazomib AND Interferon until resolution to Grade ≤ 1 or baseline. Initiate symptomatic treatment. Reduce Ixazomib by 2 dose levels and pegylated IFN by 1 dose level. If the current dose level is at a point where the above adjustment is not possible (i.e., dose adjustments have already been done), patient will be withdrawn from the study. 	
Grade 2 nausea/vomiting	
 • Continue drugs, but initiate symptomatic treatment as per Section 6.4 	

Grade 3 nausea/vomiting	
 • Hold Ixazomib AND Interferon until resolution to Grade ≤ 1 or baseline. Initiate symptomatic recommendations as per Section 6.4. • Reduce both drugs to next lower dose upon recovery. 	
Grade 4 nausea/vomiting	
 • Hold Ixazomib AND Interferon until resolution to Grade ≤ 1 or baseline. Initiate symptomatic treatment. Reduce Ixazomib by 2 dose levels and pegylated IFN by 1 dose level. If the current dose level is at a point where the above adjustment is not possible (i.e., dose adjustments have already been done), patient will be withdrawn from the study. 	
Grade 3 non-hematologic toxicity judged to be related to both study drugs	
 • Hold BOTH drugs until resolution to Grade ≤ 1 or baseline 	Symptomatic recommendations noted in Section 6.4
If not recovered to \leq Grade 1 or baseline within 4 weeks	
 • Reduce BOTH drugs to next lower dose upon return to \leq Grade 1 or baseline 	
Subsequent recurrence Grade 3 that does not recover to \leq Grade 1 or baseline within 4 weeks	
 • Hold BOTH drugs until resolution to Grade ≤ 1 or baseline • Reduce BOTH drugs to next lower dose 	Monitor closely, take appropriate medical precautions, and provide appropriate symptomatic care

Grade 3 non-hematologic toxicity judged to be related to IFN only .	
 Hold IFN ONLY until resolution to Grade ≤ 1 or baseline 	Monitor closely, take appropriate medical precautions, and provide appropriate symptomatic care

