6.13 Termination of Treatment and/or Study Participation

In the absence of treatment delays due to adverse events, treatment may continue for unlimited cycles or until one of the following criteria applies:

- Disease progression
- Intercurrent illness that prevents further administration of treatment,
- Unacceptable adverse event(s)
- Patient decides to withdraw from the study
- General or specific changes in the patient's condition render the patient unacceptable for further treatment in the judgment of the investigator.
- Withdrawl of trial support by the Sponsor

Patients will be informed that they have the right to withdraw from the study at any time for any reason, without prejudice to their medical care.

Patients who are withdrawn from the study will not be replaced.

Treatment delay of \geq 21 days for any hematologic or non-hematologic toxicity will lead to permanent treatment discontinuation.

At the time of withdrawal, all study procedures outlined for the End of Study visit should be completed. The primary reason for patient's withdrawal from the study should be recorded in the source documents and CRF.

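### The rules for stopping treatment after a toxicity delay contradict each other: 28 days against 21, investigator discretion against none, and a restart after 4 weeks against a mandatory stop

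*Combined protocol and SAP*

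**What the plan says.** Four places in the protocol bear on how long dosing may be held for toxicity.

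- **Section 6.3**, on criteria for starting a new cycle, delays both drugs when the criteria are not met. It ends: "The maximum delay before treatment should be discontinued will be 4 weeks", or as the principal investigator (PI) decides.
- **Table 6-2** (Section 6.4), in the row on delayed start of a subsequent cycle, says: "The maximum delay before treatment should be discontinued will be 3 weeks or at the discretion of the PI". The row takes its recovery criteria from Section 6.3. Although the table is titled for hematologic toxicity, the row also lists "or other non-hematologic toxicities" above a stated grade.
- **Section 6.13**, on termination of treatment, says that a delay of at least "21 days for any hematologic or non-hematologic toxicity will lead to permanent treatment discontinuation". It gives no exception.
- **Table 6-3** (Section 6.4) has rows for Grade 3 non-hematologic toxicity attributed to both drugs. Both drugs are held. If the patient has not recovered to "Grade 1 or baseline within 4 weeks", the instruction is "Reduce BOTH drugs to next lower dose upon return to" Grade 1 or less or baseline. The next row, "Subsequent recurrence Grade 3 that does not recover to" that level within 4 weeks, again says to hold and then reduce. Parallel rows apply the same rule to interferon alone when the toxicity is attributed to interferon only.

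**The concern.** These passages meet in one patient: someone whose toxicity keeps dosing on hold for three weeks or longer. Staff who follow Section 6.13 stop treatment permanently. Staff who follow Section 6.3 may still restart, and staff who follow Table 6-3 are told to restart at a lower dose even after four weeks. The documents do not say which passage takes precedence.

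Safety and exposure are at stake. One reading re-exposes a patient after prolonged toxicity and the other ends treatment for good. Two investigators could each follow the protocol and do opposite things, and either action could be logged as a deviation under the other passage.

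**Working it through.** The plan gives no statistical figure to reproduce. The check converts the limits to days and sets the passages side by side.

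**Limits in days**

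- Section 6.3: 4 × 7 = 28 days, PI may vary.
- Table 6-2: 3 × 7 = 21 days, PI may vary.
- Section 6.13: 21 days or more, permanent stop, no discretion stated.
- Table 6-3, both-drugs rows: no maximum. Its 4 weeks (28 days) triggers a dose reduction, not a stop.

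**What each passage does with a given delay**

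| Delay | Section 6.3 | Table 6-2 | Section 6.13 | Table 6-3, both-drugs rows |
|---|---|---|---|---|
| Under 21 days | Within limit | Within limit | No stop | Hold until recovery |
| Exactly 21 days | Within limit | At the limit, not past it | Permanent stop | Hold until recovery |
| 22 to 28 days | Within limit | Past limit unless PI decides otherwise | Permanent stop | Hold until recovery |
| Over 28 days | Past limit unless PI decides otherwise | Past limit unless PI decides otherwise | Permanent stop | Restart both at a lower dose on recovery |

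**Reading the table**

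1. Table 6-2 and Section 6.13 give the same length of time. They differ only on discretion and at exactly day 21.
2. The numeric conflict is therefore 28 days (Section 6.3) against 21 days (Table 6-2 and Section 6.13), a gap of 28 − 21 = 7 days.
3. Discretion is a second conflict. Section 6.3 and Table 6-2 grant it; Section 6.13 does not.
4. The third conflict lies beyond 28 days. Table 6-3 restarts both drugs in a patient whom Section 6.13 has already stopped.

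**Could difference in scope explain it?**

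Section 6.3 and the Table 6-2 row both concern a delayed cycle start, and the row borrows the Section 6.3 criteria. Section 6.3 in turn sends the reader to Tables 6-1 to 6-3 for dosing on recovery. Section 6.13 covers any toxicity, hematologic or not. The both-drugs rows of Table 6-3 hold all study treatment, so a hold of more than 28 days under them is hard to read as anything but a treatment delay under Section 6.13. Scope therefore does not separate the passages.

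The interferon-only rows are less clear. Ixazomib is not held there, and the documents do not say whether holding one drug is a treatment delay for the purpose of Section 6.13.

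**The case against.** The best defence is that the conflict is narrower than it first looks. A reader might count four incompatible limits, but the text does not support that count. Table 6-2 and Section 6.13 share one length, Table 6-3 states no maximum, and its interferon-only rows may fall outside Section 6.13. Discretion also softens the difference between Section 6.3 and Table 6-2: a PI may permit a restart after 3 or 4 weeks under either, and the late restart in Table 6-3 can be fitted to Section 6.3 in that way. All of this stands. It does not reach Section 6.13, which is mandatory and has no discretion clause, so the conflict with that section remains.

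A reader might also infer a loss of power. Section 8.1.1 counts a patient not evaluated at 8 or 16 weeks as not progression-free. Cycle 2 is due on day 29, so a 21-day delay in starting it is reached on day 29 + 21 = 50, before week 8 ends on day 56. A stop can thus precede both landmarks. The documents do not support the further step from stopping treatment to a missed assessment:

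- Section 4.4 provides follow-up for progression and survival once active treatment ends.
- Section 6.14 continues follow-up unless there is progression or consent is withdrawn.
- Note 12 to the Schedule of Events calls for imaging at off study if none was done in the previous 6 weeks.
- PFS in Sections 8.1.1 and 9 runs to progression or death, not to the end of treatment.

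The documents also give no frequency for delays of three weeks or more. Any power figure would rest on an invented rate and on an assumption that stopped patients miss their scans.

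**Conclusion.** The contradiction is in the current text and stands. It has three parts: 28 days against 21 days, PI discretion against none, and a restart after more than 4 weeks against a mandatory permanent stop. It affects any patient whose dosing is delayed by 22 days or more. At exactly day 21, Section 6.13 already stops a patient whom Section 6.3 and Table 6-2 would still allow to continue.

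The consequence is for safety, exposure and consistent conduct of the trial. Its size in patients cannot be stated, because the expected number of such delays is not given. No effect on power or on the primary endpoint is shown. The conclusion rests on one reading: that holding both drugs under Table 6-3 is a treatment delay under Section 6.13. The conflict between Sections 6.3 and 6.13 does not depend on it. This is an internal inconsistency that should be corrected, and nothing here says which limit is right.

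**What to change.** Amend Section 6.3, Table 6-2, Table 6-3 and Section 6.13 together so that they state:

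1. one maximum delay, including what happens on the boundary day;
2. whether PI discretion applies, in the same terms everywhere;
3. whether holding one drug alone counts as a treatment delay;
4. what Table 6-3 requires once that maximum has passed.

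The values and the clinical rule are for the investigators to decide. The cost is amendment wording only. Sample size, endpoints and analysis do not change.

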6.4 Management of Clinical Events

Adverse drug reactions such as thrombocytopenia, diarrhea, fatigue, nausea, vomiting, and rash have been associated with ixazomib treatment. Management guidelines regarding these events are outlined below. Further details of management of ixazomib AEs are described in Section 6 of the Ixazomib IB.

Prophylaxis Against Risk of Infection

If lymphopenia is noted, patients may be at an increased risk of infection. In particular, lymphopenia can be associated with reactivation of herpes zoster and herpes simplex viruses. Antiviral therapy such as acyclovir or valacyclovir may be initiated as clinically indicated. Other antivirals are also acceptable.

Nausea and/or Vomiting

Standard anti-emetics, including 5-HT₃ antagonists, are recommended for emesis occurring upon treatment initiation; prophylactic anti-emetics may also be considered. Dexamethasone should not be administered as an anti-emetic. Fluid deficits should be corrected before initiation of study drug and during treatment.

Diarrhea

Diarrhea should be managed according to clinical practice, including the administration of antidiarrheals such as loperamide and diphenoxylate/atropine according to the package inserts. If there is clinical suspicion for *c. difficile* infection, send stool sample for toxin assay. Avoid loperamide and diphenoxylate/atropine if there is blood or mucous in the stool, or if diarrhea is accompanied by fever. Fluid intake should be maintained to avoid dehydration. Fluid deficits should be corrected before initiation of treatment and during treatment.

Erythematous Rash With or Without Pruritus

As with bortezomib, rash with or without pruritus has been reported with ixazomib, primarily at the higher doses tested and when given with agents where rash is an overlapping toxicity. The rash may range from limited erythematous areas, macular and/or small papular bumps that may or may not be pruritic over a few areas of the body, to a more generalized eruption that is predominately on the trunk or extremities. Rash has been most commonly characterized as maculopapular or macular. To date, when it does occur, rash is most commonly reported within the first 3 cycles of therapy. The rash is often transient, self-limiting, and is typically Grade 1 to 2 in severity.

Symptomatic measures such as antihistamines or corticosteroids (oral or topical) have been successfully used to manage rash and have been used prophylactically in subsequent cycles. The use of a topical, IV, or oral steroid (eg, prednisone \leq 10 mg per day or equivalent) is permitted. Management of a Grade 3 rash may require intravenous antihistamines or corticosteroids. Administration of ixazomib (and/or other causative agent if given in

combination) should be modified per protocol and re-initiated at a reduced level from where rash was noted (also, per protocol).

In line with clinical practice, dermatology consult and biopsy of Grade 3 or higher rash or any SAE involving rash is recommended. Prophylactic measures should also be considered if a patient has previously developed a rash (eg, using a thick, alcohol-free emollient cream on dry areas of the body or oral or topical antihistamines). A rare risk is Stevens-Johnson Syndrome, a severe and potentially life-threatening rash with skin peeling and mouth sores, which should be managed symptomatically according to standard medical practice. Punch biopsies for histopathological analysis are encouraged at the discretion of the investigator.

Thrombocytopenia

Thrombocytopenia has been reported to date primarily at the higher doses tested. Blood counts should be monitored regularly as outlined in the protocol with additional testing obtained according to standard clinical practice. Thrombocytopenia may be severe but has been manageable with platelet transfusions according to standard clinical practice.

Thrombocytopenia nadirs commonly recover without intervention by the beginning of the next scheduled cycle. Ixazomib administration should be modified as noted as per dose modification recommendations in Table 6-2 when thrombocytopenia occurs. Therapy can be reinitiated at a reduced level upon recovery of platelet counts. A rare risk is thrombotic thrombocytopenic purpura (TTP), a rare blood disorder where blood clots form in small blood vessels throughout the body characterized by thrombocytopenia, petechiae, fever, or possibly more serious signs and symptoms. TTP should be managed symptomatically according to standard medical practice.

Neutropenia

Neutropenia has been reported with ixazomib. Blood counts should be monitored regularly as outlined in the protocol with additional testing obtained according to standard clinical practice. Neutropenia may be severe but has been manageable with G-CSF according to standard clinical practice. Neutropenic nadirs commonly recover without intervention by the beginning of the next scheduled cycle or with a short delay in treatment. Ixazomib administration should be modified when neutropenia occurs, as noted in the dose modification recommendations in Table 6-2. Therapy can be reinitiated at a reduced level upon recovery of absolute neutrophil counts.

Fluid Deficits

Dehydration should be avoided because ixazomib may cause vomiting, diarrhea, and dehydration. Acute renal failure has been reported with ixazomib. Fluid deficits should be corrected before initiation of study drug and during treatment and as needed during therapy. Until further information is available, intake of NSAIDs while on this protocol should be avoided.

Hypotension

Symptomatic hypotension and orthostatic hypotension with or without syncope have been reported with ixazomib. Blood pressure should be closely monitored while the patient is on study treatment and fluid deficit should be corrected as needed, especially in the setting of concomitant symptoms such as nausea, vomiting, diarrhea, or anorexia. Patients taking medications and/or diuretics to manage their blood pressure (for either hypo- or hypertension) should be managed according to standard clinical practice, including considerations for dose adjustments of their concomitant medications during the course of the trial.

Posterior Reversible Encephalopathy Syndrome

One case of posterior reversible encephalopathy syndrome (PRES) has been reported with ixazomib. While this case ultimately resolved, PRES has also been reported rarely with another proteasome inhibitor, VELCADE. PRES is characterized by headache, seizures and visual loss, as well as abrupt increase in blood pressure. Prompt diagnosis and initiation of antihypertensive and anticonvulsant therapy are important to prevent irreversible end-organ damage.

Transverse Myelitis

Transverse myelitis has also been reported with ixazomib. It is not known if ixazomib causes transverse myelitis; however, because it happened to a patient receiving ixazomib, the possibility that ixazomib may have contributed to transverse myelitis cannot be excluded.

Table 6-1 MLN908 and Pegylated IFN- α -2b Dose Adjustments during Phase II: Note levels for dose modification do not correspond with levels for dose escalation. Dose modifications will depend on the RP2D. Final dose modification schedule will be decided upon once the RP2D is determined. As an example, if the RP2D is, as expected, 4.5 mcg/kg/week of pIFN and 4.0 mg per week of Ixazomib, then the dose modification schedule will be as below.

Dose Mod Level	pIFN Dose (mg)	Ixazomib Dose (mg)
1	4.5 mcg/kg/week	4.0 mg
-1	3.0 mcg/kg/week	3.0 mg
-2	1.0 mcg/kg/week	2.3 mg
-3	Discontinue	Discontinue

Table 6-2 Ixazomib and Pegylated IFN- α -2b Dose Adjustments for Hematologic Toxicities

Within-Cycle Dose Modifications	

 • If platelet count $\leq 75 \times 10^9/L$ or ANC $\leq 0.50 \times 10^9/L$ on a Ixazomib dosing day (other than Day 1 (if Day 1, see section 6.3)) 	
 • Ixazomib dose should be withheld. • Complete blood count (CBC) with differential should be repeated at least every other day until the ANC and/or platelet counts have exceeded the prespecified values (see Section 6.3.1) on at least 2 occasions. • Upon recovery, Ixazomib may be reinitiated with 1 dose level reduction.

 • If ANC $\leq 0.50 \times 10^9/L$ and the patient is febrile (febrile neutropenia) 	
 • All treatment suspended until ANC count has exceeded the prespecified value (see Section 6.3.1) on at least 2 occasions. • Upon recovery, Ixazomib and pegylated IFN may be reinitiated with 1 dose level reduction.
Dose Modifications for Subsequent Treatment Cycles	

 • Delay of > 2 weeks in the start of a subsequent cycle due to lack of toxicity recovery as defined in Section 6.3Error! Reference source not found. • ANC $< 1.0 \times 10^9/L$, platelet count $< 75 \times 10^9/L$, or other non-hematologic toxicities $>$ Grade 2 or not to the patient's baseline condition 	
 • Hold Ixazomib until resolution as per criteria Section 6.3. • Upon recovery, reduce Ixazomib 1 dose level. • The maximum delay before treatment should be discontinued will be 3 weeks or at the discretion of the PI.
Dose Modifications for Subsequent Treatment Cycles	

 • All hematologic toxicities 	
For hematologic toxicity that occurs during a cycle but recovers in time for the start of the next cycle:
 
 ○ If dose was reduced within the cycle, start the next cycle at that same dose. ○ If due to toxicity timing, ie, during the off week for Ixazomib, a dose

Table 6-2 Ixazomib and Pegylated IFN- α -2b Dose Adjustments for Hematologic Toxicities

	
reduction was not required at that point in the cycle, reduce Ixazomib by 1 dose level at the start of the following cycle.
 
 ○ Do not reduce the dose both within a cycle and at the start of the cycle for the same most severe toxicity.
--	--

Table 6-3 Ixazomib and Pegylated IFN- α -2b Dose Adjustments (Delays, Reductions, and Discontinuations) Due to Adverse Events (Non-Hematologic Toxicities)

Grade 1 peripheral neuropathy	No action	
New or worsening Grade 1 peripheral neuropathy with pain or Grade 2 neuropathy without pain	
 ● Hold Ixazomib ONLY until resolution to Grade \leq 1 or baseline 	
New or worsening Grade 2 peripheral neuropathy with pain (not grade Grade 2 peripheral neuropathy without pain, see above for that modification) or Grade 3 neuropathy	
 ● Hold Ixazomib ONLY until resolution to Grade \leq 1 or baseline ● Reduce Ixazomib ONLY to next lower dose upon recovery 	
New or worsening Grade 4 peripheral neuropathy	
 ● Discontinuation of study drug 	
Grade 2 Rash	
 ● Symptomatic recommendations as per Section 6.4 with no dose modification 	The investigator may discuss considerations for dose modifications and symptom management with the PI
Grade 3 Rash	
 ● Hold Ixazomib ONLY until resolution to Grade \leq 1 or baseline. Initiate symptomatic recommendations as per 	

Grade 4 Rash	
Section 6.4.
 
 • Reduce Ixazomib ONLY to next lower dose upon recovery. • Hold both study drugs and discontinue study treatment for the patient. 	
Grade 2 diarrhea	
 • Continue drugs, but initiate symptomatic treatment as per Section 6.4 	
Grade 3 diarrhea	
 • Hold Ixazomib AND Interferon until resolution to Grade ≤ 1 or baseline. Initiate symptomatic recommendations as per Section 6.4. • Reduce both drugs to next lower dose upon recovery. 	
Grade 4 diarrhea	
 • Hold Ixazomib AND Interferon until resolution to Grade ≤ 1 or baseline. Initiate symptomatic treatment. Reduce Ixazomib by 2 dose levels and pegylated IFN by 1 dose level. If the current dose level is at a point where the above adjustment is not possible (i.e., dose adjustments have already been done), patient will be withdrawn from the study. 	
Grade 2 nausea/vomiting	
 • Continue drugs, but initiate symptomatic treatment as per Section 6.4 	

Grade 3 nausea/vomiting	
 • Hold Ixazomib AND Interferon until resolution to Grade ≤ 1 or baseline. Initiate symptomatic recommendations as per Section 6.4. • Reduce both drugs to next lower dose upon recovery. 	
Grade 4 nausea/vomiting	
 • Hold Ixazomib AND Interferon until resolution to Grade ≤ 1 or baseline. Initiate symptomatic treatment. Reduce Ixazomib by 2 dose levels and pegylated IFN by 1 dose level. If the current dose level is at a point where the above adjustment is not possible (i.e., dose adjustments have already been done), patient will be withdrawn from the study. 	
Grade 3 non-hematologic toxicity judged to be related to both study drugs	
 • Hold BOTH drugs until resolution to Grade ≤ 1 or baseline 	Symptomatic recommendations noted in Section 6.4
If not recovered to \leq Grade 1 or baseline within 4 weeks	
 • Reduce BOTH drugs to next lower dose upon return to \leq Grade 1 or baseline 	
Subsequent recurrence Grade 3 that does not recover to \leq Grade 1 or baseline within 4 weeks	
 • Hold BOTH drugs until resolution to Grade ≤ 1 or baseline • Reduce BOTH drugs to next lower dose 	Monitor closely, take appropriate medical precautions, and provide appropriate symptomatic care

Grade 3 non-hematologic toxicity judged to be related to IFN only .	
 Hold IFN ONLY until resolution to Grade ≤ 1 or baseline 	Monitor closely, take appropriate medical precautions, and provide appropriate symptomatic care
If not recovered to \leq Grade 1 or baseline within 4 weeks	
 Reduce IFN to next lower dose upon return to \leq Grade 1 or baseline 	Monitor closely, take appropriate medical precautions, and provide appropriate symptomatic care
Subsequent recurrence Grade 3 that does not recover to \leq Grade 1 or baseline within 4 weeks	
 Hold IFN until resolution to Grade ≤ 1 or baseline Reduce IFN to next lower dose 	Monitor closely, take appropriate medical precautions, and provide appropriate symptomatic care
Grade 4 non-hematologic toxicities judged to be related to study drug	Consider permanently discontinuing study drug	Exceptions may be made in cases in which the investigator determines the patient is obtaining a clinical benefit

Renal Impairment Dose Adjustment:

For patients whose CrCl was acceptable for study eligibility/entry per a 24 hour urine creatinine clearance, but not Cockcroft-Gault, if serum creatinine increases by 20% or more, the dose of pegylated IFN will be reduced by 25% for the particular dose level the patient is at and not re-escalated.

If a patient's CrCl was acceptable per Cockcroft-Gault for study eligibility/entry, then if CrCl drops to between 30-50 ml/min while on treatment, the dose of pegylated IFN will be reduced by 25% for the particular dose level the patient is at and not re-escalated.

Once Ixazomib or pIFN is reduced for any toxicity, the dose may not be re-escalated.

